16.3 Quantification of cell-free haemoglobin

In accordance with previous research that has indicated the advantages and precision of the Harboe method for detection of cfHb⁴⁰⁻⁴², the study will measure cfHb via a direct spectrophotometric technique in conjunction with the Harboe assay which we have previously employed⁴³⁻⁴⁵ and is an approved ISO test method for haemolysis (ISO 10993-4:2017). The measurement of cfHb will be performed within 12 hours of sample collection. To quantify cfHb via the Harboe assay, whole blood collected and anticoagulated with Ethylenediaminetetraacetic acid (EDTA), will be centrifuged at 1200 x g for 10 min. The top half of the supernatant will be added to 0.01% Na₂CO₃ (1:6) and the absorbance of each sample will be measured at 380, 415 and 450 nm using a spectrophotometer (MultiSkan GO, Thermo Fisher Scientific; MA, USA). The cfHb will subsequently be calculated from these absorbances using the Harboe method⁴⁶ (Eq. 1).

Equation 1.

$$cfHb \left(\frac{mg}{dL} \right) = \left(\frac{167.2Abs_{415} - 83.6Abs_{450} - 83.6Abs_{380}}{10} \right) \times \frac{1}{dilution\ in\ Na_2CO_3}$$

Additionally, an automated biochemistry analyzer (AU480, Beckman Coulter, USA) will be employed for a clinical measurement of haemolysis; however, the accuracy of the device is not sensitive to measurements below 50 mg/dL. Lastly, visual assessment of haemolysis will be checked, and photographs taken of each sample.

- **Device Configuration:** One of the following combinations of gauge and length
 - 22G & 1 inch
 - 22G & 1.75 inch
 - 20G & 1 inch
 - 20G & 1.75 inch
- **eCRF:** Electronic Case Report/Record Form
- **FDAAA:** FDA Amendments Act of 2007
- **GCP:** Good Clinical Practice
- **GCUH:** Gold Coast University Hospital
- **HIV:** Human Immunodeficiency Virus
- **IRB/HREC:** Institutional Review Board/Human Research Ethics Committee
- **LLAD:** Luer Lok Access Device
- **PIVC:** Peripheral intravenous catheter
- **PWD:** Pulse Wave Doppler
- **SD:** Standard Deviation
- **SOP:** Standard Operating Procedure
- **XLabS:** Experimental laboratory science group

1 Introduction

1.1 Background and Rationale

BD is investigating a specific PIVC device design factor (length and gauge) that may extend indwell time and consequently enable successful PIVC use (i.e. blood collection) throughout dwell time. Identifying device design factors that increase PIVC dwell time and reduce incidence of haemolysis would reduce associated workload costs (e.g., recollection of hemoglobin-free serum samples, PIVC reinsertion) for healthcare institutions.

1.2 Objectives

1.2.1 Primary Objectives

To assess patent indwell time for PIVCs of different length and gauge.

1.2.2 Secondary Objectives

- To assess haemolysis occurrence based on blood collection device, catheter device configuration.
- To evaluate blood draw fill time
- To determine the relationship, if any, between catheter blood draw patency indwell time and presence of intra/extravenous thrombi, catheter angle/tip location *in situ*, catheter length in vessel, vein depth from skin surface, C/V ratio, and vessel anatomy
- To evaluate changes in vessel dimensions, PIVC position (insertion angle and *in situ* tip position), and hemodynamics from baseline throughout indwell time

1.2.3 Exploratory Objectives

- To assess incidence of complications prompting device removal
- To evaluate manual flush variability (as applicable) using in-line pressure measurements

2 Study Description

2.1 Study Design

This is a single-center, open-label, multi-visit, self-controlled study design, in 40 healthy participants, randomized by gauge of peripheral intravenous catheter (PIVC) device into the lower arm cephalic vein of both arms. The purpose of this feasibility study is to assess impact of catheter length and gauge on PIVC indwell time over a multi-day (72 hour) period. This study will also evaluate the incidence of haemolysis from PIVC using a LLAD and vacutainer tube (2mL, 6mL) blood collection method compared to venipuncture from the antecubital fossa.

2.2 Study Population

Participants of clinical trials at the Clinical Trials Unit (CTU) based at the Griffith University Gold Coast campus are recruited through two primary mechanisms: 1) local advertising via digital and paper flyers; and 2) identification of suitable participants in the CTU volunteer registry (database). All advertising in the printed and audio-visual media has prior approval of the Griffith University Human Research Ethics Committee (HREC). The CTU volunteer registry has been maintained since 2015 and currently contains more than 700 volunteers.

Participants not meeting all criteria will be assessed by a medical monitor and included if patient safety is not adversely impacted.

2.2.1 Inclusion Criteria

In order to be eligible to participate in this study, an individual must meet all of the following criteria:

- Female or Male
- 18-65 years of age
- Not pregnant at time of recruitment within 48 hrs Day 1 procedures (self-reported)
- Normal coagulation results (prothrombin time 13-17 sec; activated partial thromboplastin time 27-37 sec)
- Normal platelet aggregation results for ADP, TRAP, and collagen induced maximal amplitude (>70% amplitude over 6 mins)
- Target cephalic veins readily cannulatable (i.e., $\geq \sim 2.55$ mm to obtain C/V ratio less than 45% as indicated by standard 52 of the INS guidelines)
- Able and willing to provide verbal and written consent
- Current Medicare card holder

2.2.2 Exclusion Criteria

Participants are excluded from the study if any of the following criteria apply:

- History of pro coagulative state/condition (e.g. previous deep vein thrombosis)
- Current hypertension (e.g., systolic >139 OR diastolic >89 mmHg)
- Currently on any anti-coagulant or platelet inhibitor medication. Use of NSAIDs and aspirin will be documented however not exclusionary.
- Hemophilia or any current or history of bleeding disorder or tendency
- Presence or report of current blood borne disease/infection (e.g. hepatitis, HIV, leukemia, lymphoma)
- Difficult vascular access (i.e., vein must be readily palpable and cannulatable - no less than ~ 2.55 mm diameter to maintain $\leq 45\%$ C/V ratio) as indicated by standard 52 of the INS guidelines²⁷
- Allergy or sensitivity to chlorhexidine gluconate, isopropyl alcohol, latex, or skin adhesives
- BMI <18.5 kg/m² or ≥ 35 kg/m²
- Positive results for the urine drug screen at screening or check-in (including opiates, methadone, cocaine, amphetamines)
- History or presence of alcoholism (self-reported) or drug abuse within the past 2 years
- A current or previous medical, physical, mental/cognitive disorders or anatomical conditions that, in the opinion of the investigator, would place the patient at risk, would make them unable to perform study procedures or has the potential to confound interpretation of the study results (e.g., musculo-skeletal injury, chronic back pain)
- Employed by Becton Dickinson, Teleflex Medical, Smiths Medical or B Braun (conflict of interest)

2.3 Randomization and Blinding

2.3.1 Randomization

Participants will be randomized using R statistical software (R 3.6.2 or higher). The generation of the randomization list will be conducted by a staff member not involved in data acquisition or analysis. Each randomization number will have a corresponding code (e.g., LA_20G_1.75 - indicating a Nexiva 20G 1.75 will be first inserted into the left arm). The participant will then have the other length PIVC of the same gauge inserted into the contralateral arm. Intervention kits will be created for each participant using large ziplock bags with all necessary (plus extra) consumables inside. Each kit will be separated via separate ziplock bags into consumables required for the right arm and left arm. Once the kits have been created, the appropriate randomization number will be recorded on the outside of each. Subsequently,

the corresponding code will be placed in an envelope and sealed with the randomization number written on the outside of the envelope. These envelopes will be produced in duplicate with the second envelope sealed in a locked cabinet in the CTU for the circumstance where unblinding is required. Thereafter, the randomization list excluding the corresponding code will be given to the postdoctoral research fellow for storage until a randomization number is requested for the study.

2.3.2 Blinding/Masking

Due to the concealment of intervention allocation, most staff members, other than the inserter and study manager (research assistant), will be blinded to which gauge and length catheter the participant is receiving. In order to avoid bias, sonographic data measurements (e.g., vessel diameter, C/V ratio, blood flow velocity) will be acquired on a separate day at the end of each working week. The acquisition of the sonographic measurements will be conducted by the sonographer). All concealed data will be transferred into an Excel spreadsheet that will be subsequently grouped into 2 groups in a separate Excel spreadsheet by a staff member not involved in data analysis and is unblinded. This will allow the researchers to analyze the data without having access to information about the allocation

2.3.3 Procedures for Unblinding

In the unlikely scenario of a SAE, the study manager or post-doctoral research fellow will open the duplicate envelope located in the locked cabinet of the CTU that has the randomization number written on the outside and contains the corresponding code within. The information will be provided to any personnel that require the information (e.g., the study Medical Doctor) as deemed necessary by the Principal Investigator.

2.4 Sample Size

There is limited published data investigating the impact of PIVC catheter length on indwell time; a single article was found in the literature comparing catheter survival between a BD PIVC catheter (20 gauge; 4.78 cm/1.88-inch length) and midline catheter (POWERWAND™, 19.5 gauge; 6 cm/2.3-inch length). The indwell time results for this research were utilized to calculate a sample size estimate using the routine “Survival - Two Survival Curves - Logrank Tests” available in the software PASS 2019. Based on the available dataset, a sample size of ~20 participants per PIVC length would be required, considering median failure times of catheter of different lengths of 1 and 3 days, as can be seen in Figure 2.4.1. The same calculation will be applied to investigating the impact of increased gauge, because the increased volume of catheters is similar in both condition (i.e., 1 versus 1.75 inch = 75% increased volume; 20 versus 22 gauge = 51% increased volume).

Figure 2.4.1: Details of sample size calculation

Logrank Tests

Numeric Results for the Logrank Test in Terms of Sample Size

Alternative Hypothesis: Two-Sided

Power	N1	N2	N	Haz Ratio (HR)	Ctrl	Trt	Acc-rual Pat'n	Acc-rual Time/Total Time	Ctrl Loss	Trt Loss	Ctrl to Trt		Alpha	Beta
					Med Surv Time (M1)	Med Surv Time (M2)					to Trt	to Ctrl		
0.8054	19	20	39	0.3333	1.00	3.00	Equal	0 / 3	0.0000	0.0000	0.0000	0.0000	0.0500	0.1946

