5.1.5 Vessel diameter, Catheter to vein ratio

The vessel diameter, and C/V ratio (Catheter to vein ratio) will be derived from the mean average of three cross-sectional, B-mode scans to be taken with the indwelling PIVC in view. The vessel diameter

will be calculated from the horizontal axis using the internal calculations of the ultrasound. The data will be reported as the average of the values taken from three images. The catheter diameter will be derived from the device specifications, where catheter outer diameter is reported to be 0.90 mm and 1.10 mm, respectively for 22G and 20G catheters.

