5.2.4 General Considerations

- For categorical data, count and percentage with 95% confidence interval will be calculated.
- For continuous data, average, standard error, 95% confidence interval, median, inter-quartiles, minimum and maximum will be provided.
- p-values less than 0.05 will be considered statistically significant. Multiple comparisons adjustments (Tukey's or Sydak's) will be made when appropriate
- Importance of factors/variables might be evaluated using machine learning tools such as the Boruta algorithm (random forest all-relevant approach)

- Whenever possible, effects of the following covariates will be investigated: gender, age and BMI
- Initially, all factors/variables will be included into the model as well as any two-way/three-way interactions.
- Variables or interactions which are not significant ($p\text{-value} < 0.05$) will be removed from the final model. Models adjusted with significant effects (and significant interactions if any) will be used for analysis whenever possible.
- Use of models will be preferred to non-parametric tests whenever possible.
- Residual plots for each model will be drawn and reviewed to ensure there are no systematic patterns.
- Transformation of response and/or explanatory variables will be investigated whenever modeling assumptions are not satisfied.

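### SAP 2.4 calculates power for catheter length only and carries it to gauge on a volume argument that its own figures (75% and 51%) do not support; gauge needs its own assumed hazard ratio, or a statement that it is not separately powered

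*SAP*

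**What the plan says.** Indwell time by length and by gauge is the primary objective (SAP 1.2.1), and SAP 5.2.1.1 lists one hypothesis for each. The design aims to "assess impact of catheter length and gauge on PIVC indwell time over a multi-day (72 hour) period".

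SAP 2.4 bases its log-rank calculation on length, "considering median failure times of catheter of different lengths of 1 and 3 days", and concludes that "a sample size of ~20 participants per PIVC length would be required". The software row is headed "Alternative Hypothesis: Two-Sided" and shows power 0.8054, N 19 + 20, HR 0.3333, alpha 0.05, 3 days in total, and no loss or crossover. For gauge there is one sentence: "The same calculation will be applied to investigating the impact of increased gauge, because the increased volume of catheters is similar in both condition". The figures in brackets after it are a 75% increase for 1 v 1.75 inch and "20 versus 22 gauge = 51% increased volume".

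Protocol 10.2 asks for about 20 participants per gauge on the same medians. It adds that, the study being exploratory, no formal justification of sample size is needed. Protocol 4.1 gives each gauge 20 participants with one catheter of each length. Under SAP 5.2.1.1 the main survival analysis is by device; pooling by gauge or by length is optional and depends on the results.

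**The concern.** The stated reason for reusing the length calculation is that the two volume increases are alike. They are not: 51/75 = 0.68, so the gauge increase is about two thirds of the length increase. If volume matters enough to justify the transfer, a smaller volume change gives no ground for the same HR. If volume does not matter, the transfer has no stated ground.

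At stake is how a gauge result is read. The study feeds decisions on product development (protocol 4.1), and SAP 2.6 provides an early indwell-time readout for business use. A reader of SAP 2.4 would take a non-significant gauge comparison as coming from a test with about 80% power, although no such power has been shown for gauge.

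**Working it through.** **Inputs.** From SAP 2.4: medians 1 and 3 days, HR 0.3333, N 19 + 20, 3 days of follow-up, no loss, two-sided alpha 0.05, volume increases 75% and 51%. SAP 5.2.4 confirms the level: "p-values less than 0.05 will be considered statistically significant". From protocol 4.1: 20 participants per gauge, two catheters each.

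**Formulae.** With exponential survival, expected events are d = n1(1 - 2^(-3/m1)) + n2(1 - 2^(-3/m2)), and power = Phi(|ln HR| x sqrt(d/4) - 1.96).

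**Step 1: the plan's own figure.** d = 19 x 0.875 + 20 x 0.5 = 26.6. Power = Phi(1.0986 x sqrt(26.6/4) - 1.96) = 0.809. The Lakatos method gives 0.8057 and simulation 0.807, against the stated 0.8054. The length figure reproduces.

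**Step 2: gauge by device, 20 v 20.** The documents give no link from volume to hazard, so each row is an assumption. The reference median is held at 1 day.

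| Scaling of the length effect | HR | Events | Power |
|---|---|---|---|
| ln HR x 51/75: exp(-1.0986 x 0.68) | 0.474 | 30.0 | 0.53 |
| ln HR x ln 1.51/ln 1.75 | 0.445 | 29.6 | 0.59 |
| Median gain x 51/75: 1 + 2 x 0.68 = 2.36 days | 0.424 | 29.2 | 0.64 |
| Wider: median 3 x 1.51/1.75 = 2.59 days | 0.386 | 28.5 | 0.72 |
| Wider: (1 - HR) x 51/75 | 0.547 | 31.1 | 0.39 |

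SAP 5.1.5 says that "catheter outer diameter is reported to be 0.90 mm and 1.10 mm, respectively for 22G and 20G catheters". Those diameters give (1.10/0.90)^2 = 1.494. Using 49.4/75 in the first row gives HR 0.485 and power 0.51, the lower end of the 51-64% range. Every row is below 0.80. Fixing the longer median at 3 days instead lowers the first three rows to 0.47, 0.54 and 0.59.

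**Step 3: pooled by gauge, 40 v 40 catheters.** If the two catheters of a participant are independent, the first three rows give 0.83, 0.88 and 0.91 (0.80 at HR 0.485). With an assumed within-participant correlation of 0.3, events are divided by 1.3. At HR 0.474, 60.1/1.3 = 46.2 and power = Phi(0.747 x sqrt(46.2/4) - 1.96) = 0.72. These figures also give both lengths the same reference median. If longer catheters do last longer, fewer failures fall within 72 hours and pooled power drops.

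**Step 4: HR detectable with 80% power.** By device, 20 v 20: about 0.345 (d = 27.7; 1.064 x sqrt(27.7/4) - 1.96 = 0.84). Pooled: about 0.49 if independent, about 0.43 at correlation 0.3.

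**Step 5: power over an HR range** (reference median 1 day).

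| HR | 20 v 20 | 40 v 40, independent |
|---|---|---|
| 0.333 | 0.821 | 0.983 |
| 0.40 | 0.691 | 0.935 |
| 0.45 | 0.585 | 0.868 |
| 0.50 | 0.481 | 0.771 |
| 0.55 | 0.385 | 0.655 |

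**The case against.** The strongest reply is that the plan promises no formal power for gauge. Protocol 10.2 presents the calculation as an initial estimate, SAP 2.9 sets no acceptance criteria, SAP 5.2 puts estimation on a similar footing to significance, and HRs come with 95% confidence intervals that will show imprecision. This stands, and it limits the harm. It does not make the transfer sound, because the SAP chose to extend a stated calculation to gauge and gave a reason.

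Four stronger readings are tempting, and the documents do not support them.

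- **That gauge power is a known figure below 80%.** It is not determined. No volume-to-hazard rule is given, and the anchor itself is open: the source comparison was 4.78 v 6 cm, only 26% longer (6/4.78 = 1.255), with a slightly different gauge. Tying HR 0.33 to that smaller change would point to a larger gauge effect, not a smaller one. Pooling could also reach 80% if within-participant correlation is low, though it is optional and result-dependent, so it cannot carry the stated power.
- **That the unpaired gauge comparison lowers power.** The routine used is already a two-group, unpaired log-rank calculation.
- **That 51% is an error for 49%.** SAP 2.4 does not say which dimensions it used. Rounding of 0.90 and 1.10 mm alone allows about 46% to 52% ((1.095/0.905)^2 to (1.105/0.895)^2).
- **That more participants are needed.** Nothing in a feasibility study requires 80% power for gauge.

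**Conclusion.** The point holds in limited form. The 80.5% is correct for length at HR 0.33. Its extension to gauge rests on calling 75% and 51% alike, and nothing else in either document supplies a gauge HR or power.

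On the assumption that the length effect shrinks with the volume increase and the reference median is 1 day, a by-device comparison has about 51-64% power, or 39-72% over all mappings tried. A pooled comparison has about 80-91% under the natural scalings if the two catheters are independent, and about 72% at HR 0.47 with an assumed correlation of 0.3. What does not depend on a scaling rule is that, with a 1-day reference median, 20 v 20 reaches 80% only at an HR of about 0.345 or stronger, which is almost the full length effect.

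**What to change.** Reword SAP 2.4, and protocol 10.2 to match; enrolment does not change.

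- State that the 80% figure applies to the length comparison at HR 0.33.
- Delete the volume justification for gauge.
- For gauge, do one of three things: give power over a stated HR range, such as 0.33 to 0.55, by device and pooled, with the within-participant correlation assumed; give the HR detectable with 80% power (about 0.345 by device, about 0.43-0.49 pooled depending on correlation); or state that gauge is not separately powered and will be reported as an estimate with its confidence interval.

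The scaled power figures above should not go into the SAP as facts, since they rest on an assumed mapping. The cost is a short text change and a less favourable stated power for gauge.

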2.5 Interim Analysis

A formal interim analysis is not planned. However, after 5 participants have completed their follow-up visit (V6), the in-situ catheter positions will be compared to the expected position based on the catheter lengths. Only summary statistics related to the catheter length will be provided (mean, median, percentage) and no statistical test will be performed.

2.6 Preliminary Analysis

In order to answer critically urgent business questions, a preliminary analysis will be performed by an independent statistician prior to the final database lock. This analysis will be limited to the analysis of the following specific endpoints:

- Indwell time (as described in section 5.2.1.1) and ranking of factor influencing indwell time (as described in section 5.2.2.3 by item 7)
- Haemolysis as a continuous measurement by device configuration and over time, including baseline venipuncture rate as relative comparator, as described in section 5.2.2.1 by item 1 (including the preliminary Boruta analysis)
- Rate of occurrence of Haemolysis by device configuration and over time, including baseline venipuncture rate as relative comparator, as described in section 5.2.2.1 by item 2 (including the preliminary Boruta analysis)
- Thrombus observation by device configuration over time, as described in section 5.2.2.3 by items 1, 2, 3, 4 and 7
- Incidence of failure modes for device removal, as described in section 5.2.1.2

The results of the preliminary analysis will be communicated by the independent statistician to [name] (Associate Director - Biomedical Engineering) who will be responsible for sharing them with [name] (Director - Product Development Engineering), select MDS designees, and [name] (Director/Principal Scientist - Parenteral Research). Preliminary analysis will not be shared beyond those required for making time-critical business decisions on behalf of the MDS business unit.

Every GCD employee involved in the study execution, especially the lead study statistician, as well as all site employees involved in the study execution, will remain blinded to the results of this preliminary analysis until database lock.

It is understood by all parties that the results of this primary analysis will be subject to confirmation after database lock and fulfillment of all the processes related to data quality described in the Data Management Plan.

2.7 Study Procedure

The time-windows for collection of the primary, secondary and exploratory endpoints are detailed in Table 2.7.1.

The primary endpoint data (catheter dwell time) and exploratory endpoint data (PIVC complications) will be collected over 7 time-windows (see text highlighted in orange on Table 2.7.1). The secondary endpoint data (cfHb, blood draw time) will be collected over 8 discrete timepoints (including baseline, see text highlighted in red on Table 2.7.1).

All other secondary endpoint data (e.g., blood flow velocity, vessel diameter), except incidence of extravenous thrombus (assessed once the catheter is removed), will be collected over 15 timepoints (see text

highlighted in blue and grey on Table 2.7.1). Please note that the cells that indicate ‘Day’ in Table 1 are indicating the interventional visit days and are not inclusive of the screening visit or follow-up visit.

The flush pressure profile exploratory endpoint data will be collected over 7 timepoints (see text highlighted in blue on Table 2.7.1).

Table 2.7.1: List of sampling time points for primary, secondary, and exploratory endpoints. cfHb: cell-free hemoglobin; TIP: catheter tip position; BFV: blood flow velocity; C/V: catheter to vein ratio; PRES: in vivo pressure; PIVC: peripheral intravenous catheter; FILL: blood draw fill time. Time T+00:00 is the time of insertion

Day	Visit	Timepoint code	Approximate (hh:mm)	Time	Measurements taken
Day 1	Baseline	D1.1	T-00:60		TIP, BFV, C/V via ultrasound (no indwelling catheter)
		D1.2	T-00:40		cfHb via venipuncture
	Morning	D1.3	T+00:15		TIP, BFV, C/V via ultrasound, PRES via PIVC during flush
		D1.4	T+00:25		cfHb, FILL via PIVC
	Afternoon	D1.5	T+00:35		TIP, BFV, C/V via ultrasound
		D1.6	T+06:00		TIP, BFV, C/V via ultrasound, PRES via PIVC during flush
		D1.7	T+06:15		cfHb, FILL via PIVC
		D1.8	T+06:25		TIP, BFV, C/V via ultrasound
Day 2	Morning	D2.1	T+24:00		TIP, BFV, C/V via ultrasound, PRES via PIVC during flush
		D2.2	T+24:15		cfHb, FILL via PIVC
	Afternoon	D2.3	T+24:25		TIP, BFV, C/V via ultrasound
		D2.4	T+30:00		TIP, BFV, C/V via ultrasound, PRES via PIVC during flush
		D2.5	T+30:15		cfHb, FILL via PIVC
		D2.6	T+30:25		TIP, BFV, C/V via ultrasound
Day 3	Morning	D3.1	T+48:00		TIP, BFV, C/V via ultrasound, PRES via PIVC during flush
		D3.2	T+48:15		cfHb, FILL via PIVC
	Afternoon	D3.3	T+48:25		TIP, BFV, C/V via ultrasound
		D3.4	T+54:00		TIP, BFV, C/V via ultrasound, PRES via PIVC during flush
		D3.5	T+54:15		cfHb, FILL via PIVC
		D3.6	T+54:25		TIP, BFV, C/V via ultrasound
Day 4	Morning	D4.1	T+72:00		TIP, BFV, C/V via ultrasound, PRES via PIVC during flush
		D4.2	T+72:15		cfHb, FILL via PIVC
		D4.3	T+72:25		TIP, BFV, C/V via ultrasound

